#### Loss of PASI 75 response over time

The loss of PASI 75 response during RW period will be repeated. In addition, the secukinumab treatment groups will also be compared, i.e. a Cox proportional hazards regression will be fitted as described above including all four treatment groups. Placebo (secukinumab 150 mg in core studies) and Placebo (secukinumab 300 mg in core studies) will be compared as well as secukinumab 150 mg and secukinumab 300 mg.

#### Loss of IGA 0 or 1 response over time

Novartis	Confidential	Page 48
RAP Module 3	9-Apr-2018 (1:15)	Secukinumab / AIN457A2302E1

Loss of IGA 0 or 1 response over time will be analyzed analogously to the loss of PASI 75 response, but it will be restricted to the subset of subjects who have been IGA 0 or 1 responder at Week 52.

# For subjects who were re-treated after relapse with secukinumab 150 mg or 300 mg

#### PASI 50, PASI 75, PASI 90, PASI 100 and IGA 0 or 1 response over time

Descriptive statistics will be provided from relapse until week 156. Summary statistics for PASI 50, PASI 75, PASI 90, PASI 100 and IGA 0 or 1 response by visit will be provided similar as for RW period.

## **1.9.7** Risk set, timing and censoring for time to event analysis

Subjects at risk, timepoint "0" and censoring will be defined as described in Table 1-14 below.

#### Table 1-64 Time to event: definition of risk set, timing and censoring by variable

Variable: Time to	Risk set	Time = 0	Time of event	Censoring	Psoriasis ConMed	Informative censoring
Loss of PASI 75 response	All PASI 75 responders at Week 52 per analysis visit AND entering RW period as per CRF disposition page	Week 52 per analysis visit	Date of 1 st visit with OBSERVED loss of PASI 75 response (i.e. no imputation for missing values)	Last available visit up to Week 68 per analysis visit for PEA & End of RW period for secondary analysis	Event (if the subject took psoriasis ConMed, the subject is considered as having lost response)	Study phase discontinuati on with reason "lack of efficacy"

[figure not shown]
Novartis		
RAP Module 3		

## Confidential 9-Apr-2018 (1:15)

Page 49 Secukinumab / AIN457A2302E1

Variable: Time to	Risk set	Time = 0	Time of event	Censoring	Psoriasis ConMed	Informative censoring
Loss of IGA mod 2011 0 or 1 response	All IGA 0 or 1 responders at Week 52 amongst PASI 75 responders as per analysis visit AND entering RW period as per CRF disposition page	Week 52 per analysis visit	Date of 1 st visit with OBSERVED loss of IGA mod 2011 0 or 1 response (i.e. no imputation for missing values)	Last available visit up to Week 68 per analysis visit for PEA & End of RW period	Event (if the subject took psoriasis ConMed, the subject is considered as having lost response)	Study phase discontinuati on with reason "lack of efficacy"
Relapse (in follow-up period)	All subjects who were PASI 50 responders (based on OBSERVED data)at least once during the RW or treatment period	Date of last active treatment or last secukinuma b placebo administrati on	Date of 1 st visit with OBSERVED relapse (i.e. no imputation for missing values) after time = 0	End of follow-up period as per CRF disposition page	Event (if the subject took psoriasis ConMed, the subject is considered as having experienced relapse)	Study phase discontinuati on with reason "lack of efficacy"

ConMed: Concomitant medication Psoriasis ConMed is defined in MAP appendix

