**For the subjects classified as PASI 75 responders at Week 52 the study consists of 5 or 6 periods**

(i) screening period: is the duration between signing the informed consent form (ICF) and randomization registered with Interactive Response Technology (IRT).

(ii) randomized withdrawal period: the duration of randomized withdrawal period for each subject is different i.e., starting from Week 52 until the subject experiences the relapse or up to Week 156.

(iii) treatment period: A placebo subject experiencing a relapse during the withdrawal period will receive four doses of secukinumab s.c. at weekly intervals followed by secukinumab s.c. every four weeks. Subjects on secukinumab in the randomized withdrawal period who have a relapse, will be given four weekly doses of placebo s.c. Following the loading doses, subjects will continue on secukinumab treatment at 4 week intervals. Any subject, whether randomized to placebo or active treatment, will only be treated once with the weekly loading dose regimen. For subsequent relapses, patients will continue on secukinumab at 4 week intervals. Week 152 will be the last dose of the blinded treatment period. At Week 156 subjects will enter the open label period. The site must call IRT in order to unblind the subject to enter the open label period prior to performing the dosing.

(iv) open label period: The treatment will be unblinded at Week 156 and the subjects will enter the open label period. During this period, the subjects will be given pre-filled syringes and instructed to perform self-injection at home every 4 weeks and return to the site every 12 or 16 weeks (please see [Table 6-1](#) Assessment schedule). The first open label dose will be given at the site at Week 156. Subjects previously randomized to receive 150 mg secukinumab may continue with 150 mg secukinumab open label or may switch to 300 mg s.c. at the discretion of the investigator. Subjects previously randomized to 300 mg secukinumab will continue with 300 mg secukinumab open label. Subjects receiving placebo during randomized withdrawal period will start secukinumab 150 mg or 300 mg at the discretion of the investigator. Any subject on 150 mg s.c. may be switched to 300 mg s.c. at the discretion of the investigator at a regularly scheduled visit. Note: the Week 244 visit will be the last scheduled visit at which the subjects will be allowed to switch to 300 mg dose. Decreasing the dose from 300 mg to 150 mg is not allowed.

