**For the subjects classified as partial responders at Week 52 the study consists of 4 or 5 periods**

(i) screening period: is the duration between signing the informed consent form (ICF) and randomization registered with IRT.

(ii) treatment period: starting from the randomization visit at Week 52 continuing through Week 156. The patients will receive secukinumab s.c. every 4 weeks at the dose which they were originally assigned in the core study. At Week 156 they will enter the open label period. For subjects who don't enter the open label period, Week 156 visit is the EoT.

(iii) open label period: At Week 156, the subjects will be given pre-filled syringes and starting Week 160 the subjects will be asked to perform self-injection at home every 4 weeks and return to the site every 12 or 16 weeks (please see [Table 6-1](#) Assessment schedule). Also, at Week 156 subjects receiving 150 s.c. may be switched to 300 mg s.c. if the subject and the PI agree that the subject would benefit from the higher dosage at a regularly scheduled visit. The subjects will receive the last dose of the study medication at Week 256.

(iv) follow-up period (for all subjects): treatment free period (Week 264 to Week 268).

(v) follow-up 2 period: treatment free period only for patients who prematurely discontinued treatment. All subjects who prematurely discontinue treatment should complete all assessment of Week 260 (end of treatment visit) and of the follow-up period visits (Weeks 264 and 268). Subsequently, adverse events and use of concomitant medication will be evaluated by the investigator through telephone calls every 3 months for a duration of 4 years from the time when subject has been enrolled into CAIN457A2302E1 study.

**NOTE:** *Partial responders DO NOT participate in the randomized withdrawal and DO NOT receive any loading dose even if they experience a full relapse (a loss of >50% of the maximum PASI gain compared to baseline of the core study).*

Subjects classified as **partial responders** at Week 52 of the core studies will continue the same treatment dose in PFS (secukinumab s.c. 150 mg or 300 mg) that they were receiving at the time of completing the maintenance period (Week 52) in the core study.

In the **follow-up period** (Week 264 to Week 268) all subjects will visit the study site for safety and efficacy assessments while being off-treatment.

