#### Table 1-2 The PASI scoring system

\* Percentage (not score) of body region (not whole body) affected will be entered in the eCRF

+ Neck is assessed as part of the Head (H) body region.

‡ Axillae and groin are assessed as part of the Trunk (T) body region.

§ Buttocks are assessed as part of the Lower limbs (L) body region.

The following definitions are possible efficacy evaluations that can be used in clinical trials in psoriasis (CHMP/EWP/2454/02, 2004):

- **PASI non response:** subjects achieving <50% improvement (reduction) in PASI score compared to baseline are defined as PASI non responders
- **Partial response**: subjects achieving ≥ 50% improvement (reduction) in PASI score but less than 75% compared to baseline are defined as partial responders
- **PASI 50 response**: subjects achieving ≥ 50% improvement (reduction) in PASI score compared to baseline are defined as PASI 50 responders
- **PASI 75 response**: subjects achieving ≥ 75% improvement (reduction) in PASI score compared to baseline are defined as PASI 75 responders

Novartis	Confidential	Page 32
RAP Module 3	9-Apr-2018 (1:15)	Secukinumab / AIN457A2302E1

- **PASI 90 response**: subjects achieving ≥ 90% improvement (reduction) in PASI score compared to baseline are defined as PASI 90 responders
- **PASI 100 response**: complete clearing of psoriasis (PASI=0)
- **Relapse**: when the achieved maximal PASI improvement from baseline PASI in core is reduced by >50%
- **Rebound-like event**: defined as increase of PASI of more than 25% from baseline value or occurrence of new pustular, new erythrodermic or more inflammatory psoriasis **after** stopping therapy
- Rebound: defined as rebound like event occurring within 8 weeks of stopping therapy

The analysis of rebound will be done for the follow-up period.

The number and percentage of subjects experiencing rebound and rebound like events will be presented by treatment group as follows:

- For rebound, all assessments done up to 8 weeks will be summarized.
- Similarly for rebound like events, all assessments done up to 12weeks will be summarized.
  - 1. Rebound up to 8 weeks: For this time-point the worst outcome (i.e. rebound like event=yes) prior to this cut-off is considered (e.g. if a subject had >25% PASI increase at Week 260, but not at Week 264 the subject would be considered as rebounder for this "up to 8 week timepoint").

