### Relapse

Relapse will be analyzed analogously to loss of PASI 75 response in the follow-up period.

A listing of these subjects will also be provided.

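### The follow-up relapse analysis does not require subjects to be out of relapse at the last dose, so relapse that began on treatment and persists is counted as relapse in follow-up

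*SAP*

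**What the plan says.** SAP 1.9.7 refers the risk set, time zero and censoring of every time-to-event analysis to Table 1-14. The row for relapse in follow-up has three relevant parts:

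- **Risk set:** "All subjects who were PASI 50 responders (based on OBSERVED data)at least once during the RW or treatment period".
- **Time zero:** the date of the last dose, whether active drug or placebo.
- **Event:** the date of the first "visit with OBSERVED relapse (i.e. no imputation for missing values) after time = 0".

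SAP 1.9.1.1 defines relapse as occurring "when the achieved maximal PASI improvement from baseline PASI in core is reduced by >50" percent. The reference is the best improvement the subject has ever reached, not the PASI at the last dose. The analysis belongs to the final analysis: SAP 1.9.6 says "Relapse will be analyzed analogously to loss of PASI 75 response in the follow-up period".

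The protocol allows dosing to continue during relapse. The synopsis says of PASI 75 responders who have already been through the relapse regimen: "For subsequent relapses, patients will continue on secukinumab at 4 week intervals". Partial responders "DO NOT receive any loading dose even if they experience a full relapse" and stay on their dose.

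**The concern.** A time-to-event analysis of relapse normally starts with subjects who could still have the event. Here entry needs one PASI 50 response at some point, possibly years before the last dose. Entry to the study already required PASI 50 or better at Week 52 (Protocol 4.1), so the condition removes few subjects. Nothing requires the subject to be out of relapse at time zero, or the relapse to be new.

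The affected subjects are those who have relapsed a second time and continued 4-weekly dosing, and partial responders in full relapse. If such a subject is still in relapse at the first visit after the last dose, the event rule is met although nothing has changed since dosing stopped. These events fall at the start of the curve and look like rapid relapse on cessation. If on-treatment failure differs between groups, so does the distortion.

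**Working it through.** The plan gives no figure for this analysis, so there is none to reproduce. The check applies the SAP's rules to example subjects and then shows how the estimate responds to assumed shares.

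**1. Example subjects (invented values).** Share of gain lost = 1 − (baseline − current) / (baseline − best).

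- *PASI 75 responder, second relapse.* Core baseline 20, best 4, PASI 13 at last dose. Best gain 16 (80%), current gain 7. Share lost = 9/16 = 56%, so the subject is in relapse at the last dose. The subject is in the risk set. An unchanged PASI of 13 at the next visit is scored as a follow-up relapse.
- *Partial responder.* Core baseline 24, best 11, PASI 18 at last dose. Best gain 13 (54%), current gain 6. Share lost = 7/13 = 54%, with the same result.

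**2. Comparison within Table 1-14.** The row for loss of PASI 75 admits only PASI 75 responders at Week 52, which is its time zero. The row for loss of IGA 0 or 1 likewise requires that response at Week 52. Only the relapse row has no condition on status at time zero.

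**3. Effect on the estimate.** Let q be the share of the risk set in relapse at the last dose and still in relapse at the first later visit. Let p be the true follow-up relapse rate in the rest. Neither is given in the documents for this analysis.

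As written: q + (1 − q)p. With the risk set restricted: p. Excess: q(1 − p), which is never negative.

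| q (assumed) | p (assumed) | As written | Restricted | Share of events pre-existing |
|---|---|---|---|---|
| 2% | 10% | 11.8% | 10% | 17% |
| 5% | 10% | 14.5% | 10% | 34% |
| 10% | 10% | 19.0% | 10% | 53% |
| 10% | 20% | 28.0% | 20% | 36% |
| 20% | 30% | 44.0% | 30% | 45% |

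If two groups shared p = 10% but had q = 2% and q = 10%, the analysis would show 11.8% against 19.0%. That is a 7.2-point difference with no difference in relapse after stopping.

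**4. Which PASI can be used to screen.** In the double-blind period PASI is assessed before dosing at scheduled visits (Protocol 6, order of assessments), so a same-day value is normally available. In the open-label period PASI is taken at site visits. Table 6-1 and its footnote 19 show no scheduled site visit between Weeks 244 and 260, and the last dose is at Week 256. For open-label completers the last scheduled PASI before the last dose is therefore 256 − 244 = 12 weeks old.

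**The case against.** **The analogy may already solve it.** SAP 1.9.6 analyses follow-up relapse by analogy with loss of PASI 75, and SAP 1.9.4 censors at day 0 subjects randomized without a PASI 75 response. On this view the text is only unclear. That does not remove the problem. The day-0 rule sits under the heading for the randomized-withdrawal re-run and says nothing about relapse status at last dose. SAP 1.9.7 sends the risk set to Table 1-14, whose relapse row has its own wording. The rule does show that the restriction fits the SAP's practice elsewhere.

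**The purpose is not stated.** No passage says that this curve estimates new relapse after stopping secukinumab. Protocol 9.5.1 speaks only of additional analyses of relapses observed in follow-up, and the relapse objective in Protocol 2.2 is a comparison with placebo in Week 52 responders. This stands and limits the importance of the point. A reader would still naturally take a curve timed from the last dose as relapse after stopping.

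**Lack-of-efficacy discontinuations.** A reader might infer that these are miscounted in the same way. The documents do not support that without qualification. SAP 1.9.4 treats drop-out for lack of efficacy as failure at drop-out, and the relapse row lists it under informative censoring. Some counting of treatment failure is thus a stated choice.

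**Time zero.** Because the last dose may be placebo, a reader might infer that the clock should move to the last active dose. That would create a new bias. Placebo subjects who never relapse and decline open label enter follow-up after Week 156, but their last active dose was in the core study, before Week 52. They would carry about two years (156 − 52 = 104 weeks) in which no follow-up event could occur. For relapsers on active drug, the blinded placebo injections fall one to three weeks after the relapse visit (Protocol Table 3-1), so they shift time zero by at most three weeks.

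**Small impact.** The SAP already plans a listing of these subjects, and relapse that resolves before the next visit is not miscounted. Both points are fair, but a listing does not correct the estimate.

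**Conclusion.** The point stands as a defect in a risk-set definition. As written, persisting relapse from the treatment period is counted as follow-up relapse, and the early estimate is biased upward. The direction follows from the rules.

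The size is unknown. It depends on the share in relapse at last dose and on how much of that relapse persists, and the documents give neither. The table above is illustrative. A reader might combine assumed shares with the protocol's prediction of 10% full relapse after four months to quote an expected inflation. That is not supported: the prediction (Protocol 3.3) is for Week 52 responders and is described there as having unquantifiable uncertainty. Open-label entry also required judged benefit (Protocol 4.1), which makes the highest assumed shares doubtful for open-label completers.

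A reader might also infer that the trial's main result is affected. It is not: the analysis is secondary and outside the testing strategy (SAP 1.9.3), and the primary endpoint and its power do not depend on it. The correction should be made because the estimate could mislead and the change is cheap.

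**What to change.** In the relapse row of SAP Table 1-14:

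1. Add to the risk set the condition that the subject is not in relapse at the last available PASI on or before the last study dose.
2. Report subjects already in relapse at that assessment as a separate count by treatment group.
3. State that for open-label completers this PASI is normally Week 244, about 12 weeks before the Week 256 dose, so some relapse that began on treatment between those weeks will still be counted.
4. Keep time zero at the last study dose. Show subjects whose last dosing was withdrawal placebo (never re-treated) separately from those stopping secukinumab.

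The data are already collected, and the change is limited to this row, a note and the display by last treatment. The cost is a somewhat smaller risk set and imperfect classification from an older PASI. A subject in relapse at Week 244 who recovered before Week 256 would be left out of the risk set, and one who relapsed between those weeks would stay in.

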If they refuse to return for the needed assessments in the follow-up period or are unable to do so, every effort should be made to contact them or a knowledgeable informant by telephone or by sending appropriate correspondence (i.e. certified letter) immediately. At this contact, the safety (e.g., potential occurrence of AE or SAE) and the primary reason for a subject's premature withdrawal should be determined.

At a minimum, subjects will be contacted for safety evaluations during the 12 weeks following the last dose of study treatment, including final contact at the 12 week point. Documentation of attempts to contact the subject should be recorded in the subject record.

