## 1.9.4 Handling of missing values/censoring/discontinuations

#### For the analyses re-run during RW period

The loss of PASI 75 response during RW period will be re-run. The subjects who have no lost PASI 75 response during RW will be considered as censored observations. Subjects who have not lost PASI 75 response but with missing values during RW will be considered as censored at prior available visit. Subjects who administered psoriasis concomitant medication (as per [MAP Appendix]), will be considered as failures at time of first administration if this occurred before the loss of PASI 75. Subjects who did not have PASI 75 response but randomized in RW period will be censored at day 0. Subjects with missing values at week X (X <156) and who have not lost PASI 75 response earlier, will be censored at week X (if they have not dropped out due to lack of efficacy or not administered psoriasis concomitant medication). Subjects who drop-out due to lack of efficacy will be considered as failure at time of drop-out. If drop-out was due to other reason, subjects will be considered as censored at time of drop-out. Intermediate missing values will not be considered.

Other time-to-event analyses will be handled analogously. For imputation techniques, please refer to Table 1-16.

For other analyses (not time to event) missing values with respect to response variables based on PASI score and IGA mod 2011 score will be imputed with multiple imputation regardless of the reason for missing data (e.g., premature study discontinuation, missed visit, administrative issues).

Following the intent-to-treat principle for subjects who prematurely discontinue treatment, but who are observed in the follow-up period, efficacy data collected in follow-up periods will be linked to planned but missed study visits as well, following imputation schemes described in Sections 1.5.4.1 and 1.9.4.2. (e.g., if a subject discontinues treatment at Week 56, but has follow-up visit F4, the PASI score observed at Visit F4 might be used for Week 60 assessments).

Novartis	Confidential	Page 39
RAP Module 3	9-Apr-2018 (1:15)	Secukinumab / AIN457A2302E1

For rebound and relapse no imputed data will be used and analyses will be based on observed data only.

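### SAP Table 1-14 censors follow-up relapse at a CRF date that needs no PASI, so unexamined time can count as relapse-free

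*SAP*

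**What the plan says.** The rule is in the relapse row of SAP Table 1-14 (section 1.9.7):

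- Risk set: "All subjects who were PASI 50 responders (based on OBSERVED data)at least once during the RW or treatment period". No PASI after the last dose is required.
- Time zero: "Date of last active treatment or last" placebo administration.
- Event: the date of the first "visit with OBSERVED relapse (i.e. no imputation for missing values) after time = 0".
- Psoriasis co-medication: "Event (if the subject took psoriasis ConMed, the subject is considered as having experienced relapse". This route needs no PASI.
- Informative censoring: discontinuation of the study phase for lack of efficacy. The table does not say how it enters the analysis; SAP 1.9.4 makes it a failure at drop-out in the randomized-withdrawal (RW) analyses.
- Censoring: "End of follow-up period as per CRF disposition page".

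Three other places bear on the censoring date. SAP 1.9.6 has follow-up relapse analysed in the same way as loss of PASI 75. The loss-of-PASI-75 row of Table 1-14 censors at the last available visit for the Week 68 analysis. SAP 1.9.4, under the rules for the RW re-runs, says "Subjects who have not lost PASI 75 response but with missing values during RW will be considered as censored at prior available visit", extends its rules by analogy to other time-to-event analyses, and adds "For rebound and relapse no imputed data will be used and analyses will be based on observed data only".

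Protocol section 6 foresees subjects who refuse or cannot attend follow-up. For them, "subjects will be contacted for safety evaluations during the 12 weeks following the last dose of study treatment", with a last contact at Week 12.

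**The concern.** Apart from co-medication and lack of efficacy, an event can be detected only where there is a PASI, while time at risk runs to an administrative date. A subject last examined at Week 260, or never examined after the last dose, can add event-free time during which no PASI-based relapse could have been seen. In a Kaplan-Meier estimate this acts like assuming no relapse over that time.

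The SAP also gives no single answer. A programmer working from Table 1-14 uses the CRF date; one working from section 1.9.6 and the loss-of-PASI-75 rules could use the last available visit. A subject who never enters the follow-up period may have no end-of-follow-up date, and the SAP does not cover that case.

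The stake is the relapse rate after stopping treatment. Table 1-9 marks relapse for the final analysis and Table 1-4 assigns it to the follow-up period.

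**Working it through.** **1. Length of the window.** Protocol section 3.1 puts the last follow-up visit 12 weeks after the last dose. This reproduces three ways: 268 - 256 = 12 weeks; 2016 h / 168 = 12 weeks (blood log, Protocol Appendix 2); and, in SAP study days, Week 268 is Day 1513 and Week 256 is Day (256 - 52) x 7 + 1 = 1429, so 1513 - 1429 = 84 days. Post-dose PASI visits fall at 4, 8 and 12 weeks (Weeks 260, 264, 268).

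**2. Inputs.** The documents give neither the relapse rate r at 12 weeks nor the share m of unexamined subjects. For r, 10% is the model prediction of full relapse at four months (Protocol 3.3). The figure of 33.3% is observed loss of PASI 75 at 12 weeks in the earlier study cited there; it is not relapse and serves as a high illustration. For m, 5% to 20% is assumed; the 15% drop-out assumed for the core studies (Protocol 9.7) only helps to centre that range. Missingness is taken as unrelated to relapse, and relapse as accruing evenly over the three visits.

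**3. Worst case.** No PASI after the last dose, CRF date at 12 weeks, no offsetting event. Only the examined share 1 - m can produce events, but everyone stays at risk, so the estimate is r(1 - m). Censoring at the last PASI returns r.

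| m (assumed) | r = 10% | r = 33.3% |
|---|---|---|
| 5% | 9.5% | 31.7% |
| 10% | 9.0% | 30.0% |
| 15% | 8.5% | 28.3% |
| 20% | 8.0% | 26.7% |

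**4. What shrinks or reverses it** (m = 15%).

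- Week 260 PASI done, later visits missed: a third of these subjects' relapses are seen, so the estimate is r(1 - 2m/3): 9.0% for r = 10% and 30.0% for r = 33.3%.
- Earlier CRF date, r = 33.3%: the visit hazards in examined subjects are 1/9, 1/8 and 1/7. With a 4-week date, survival is (1 - 0.85/9) x 7/8 x 6/7 = 0.679, giving 32.1%. With an 8-week date it is (1 - 2 x 0.85/9) x 6/7 = 0.695, giving 30.5%. With a date before the first visit there is no loss.
- Half of the unseen relapses captured as co-medication or lack of efficacy, r = 10%: 0.85 x 10% + 0.15 x 5% = 9.25%.
- Co-medication in 20% of unexamined subjects, r = 10%: 0.85 x 10% + 0.15 x 20% = 11.5%, which is above the true rate.

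**5. The remedy tested the same way.** Take r = 10%, m = 15%, and half of the unseen relapses captured without a PASI. Censoring the remaining unexamined subjects at time zero while keeping the captured events gives (0.085 + 0.0075) / (0.85 + 0.0075) = 10.8%, against 9.25% under the CRF date and a true 10%.

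**The case against.** A reader might infer that every unexamined subject is counted as relapse-free for 12 weeks and that relapse is therefore understated. The documents do not support that:

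- Co-medication counts as relapse without a PASI, and lack-of-efficacy discontinuation is singled out. Subjects who flare are the ones most likely to be caught this way, and co-medication is also asked about by telephone in follow-up 2. The net direction is therefore not fixed. The offset need not be complete, however: Protocol 5.5.8 keeps the Table 5-1 treatments prohibited during follow-up, exempting only follow-up 2, and the lack-of-efficacy route needs that reason on record.
- Protocol section 6 requires safety contact to Week 12 but does not say that this contact sets the disposition date. Under Protocol 5.5.9, subjects who fail to return may be considered withdrawn, so their date may be early.
- Completers have a PASI at Week 268, so their CRF date and last PASI should roughly coincide. Those who stop treatment early are scheduled for the Week 260 assessments about four weeks after the last dose.

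A reader might also infer that the cell breaches the observed-data rule. It does not do so literally, since no PASI is imputed. The prior-available-visit sentence belongs to the RW re-runs, and the same paragraph also censors at week X or at drop-out. The loss-of-PASI-75 row names the end of the RW period for its secondary analysis. What stands is that the SAP does not fix one censoring date.

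A distortion between dose groups is possible if missed visits differ by group, but nothing in the documents shows that they will.

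The objection that last-PASI censoring can bias upward is correct (step 5). It calls for a sensitivity analysis; it does not justify keeping a date unrelated to examination.

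**Conclusion.** The point holds as a possible understatement and an internal inconsistency. Table 1-14 lets subjects without a co-medication or lack-of-efficacy event remain at risk past their last PASI, for at most a nominal 12 weeks. The worst-case relative loss equals m. At the only relapse rate that the documents offer (10%, a model prediction at four months), that is 0.5 to 1.5 percentage points for m = 5% to 15%. It is less with earlier CRF dates or a Week 260 PASI, and of opposite sign if co-medication among unexamined subjects exceeds r. These figures rest on assumed m and r, missingness unrelated to relapse, and even accrual; the actual size cannot be derived from the documents.

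Relapse is a secondary variable outside the testing strategy (SAP 1.9.3). The primary endpoint, alpha and sample size are not touched. The change is worth making because the current wording can be programmed in two ways.

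**What to change.** In the relapse row of SAP Table 1-14, replace the censoring cell with: *date of the last observed PASI after time zero, up to the end of the follow-up period; time zero if there is none.* Then:

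- Keep the co-medication and lack-of-efficacy cells, and state that each counts as an event on its own date whether or not a PASI exists.
- Report by treatment group the number of subjects with no post-dose PASI, and the number of events resting on co-medication or lack of efficacy alone.
- Present CRF-date censoring as a sensitivity analysis, with a stated rule for subjects who never enter follow-up.
- Align SAP 1.9.4, 1.9.6 and Table 1-14 on the same date.

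No new data are needed. The cost is a small wording change, one additional run, slightly wider confidence intervals, and a possible slight upward bias from events recorded without a PASI. Showing both censoring dates makes the size of that effect visible.
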